2.5. Baseline and Endpoint

The baseline analysis visit is defined as the last assessment before the first intake of the study drug, with the possible exception for height, weight, viral load results from the central lab testing and the hospital recovery scale (HRS). Height and weight are only recorded once, at screening/baseline visit, and the values recorded at this visit will be allocated to the baseline analysis visits irrespective of start of study drug. For viral load, if no measurement is available prior to first dose of study drug, then the first result from the central lab testing obtained up to and including 30 minutes after first dose of study drug will be considered as the baseline assessment and will be flagged in the analysis dataset. The baseline HRS is defined irrespective of the time of the start of study drug, and is covering the screening/baseline/day 1 visit which may be performed over two days as defined per protocol. Baseline HRS will be assigned to Day 1.

As specified in the protocol, an ECG recording within 1 calendar day before signing of the ICF/assent form can be used as baseline ECG requirement, if no ECG measurement was performed between signing ICF and first study drug intake.

For programming purposes the baseline record will be doubled in the ADAM datasets, the doubled record will be renamed with AVISIT = 'Baseline', AVISITN = 0 and will be assigned to the treatment phase.

For vital signs, NEWS2, ECG and central laboratory data the last study visit (Endpoint) is defined as the last scheduled study visit/timepoint and will be either the final study visit (day 28) or the safety follow-up visit.

For viral phenotyping, the last visit (Endpoint) is defined as the last study visit/timepoint for which an EC₅₀ and/or IC₅₀ result is available (including unscheduled visit results).

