5.1. Analysis Specifications

5.1.1. Level of Significance

The population used for the evaluation at the final analysis will depend on the outcome scenario of the interim analysis: i.e.; scenario 1: continue with the full study population or scenario 2: continue only with the subjects with an onset of symptoms less than 72 hours before first study drug intake. Tables/graphs/listings will account for the selected scenario.

As a confirmatory strategy, to account for multiplicity in the statistical evaluation of the most important efficacy endpoints, in either scenario, a combination of hierarchical testing and the Bonferroni-Holm testing procedure will be applied to control for the overall Type I error rate at the 5% level. The following endpoints are included in the confirmatory strategy:

1. Hospital recovery scale at Day 6, ie, primary endpoint
2. Incidence in post-baseline complications
3. Time to hospital discharge
4. Time from ICU admission to ICU discharge
5. Time to return to daily activities
6. Time from start of mechanical ventilation to end of mechanical ventilation
7. Rate of re-hospitalization

First, the primary endpoint will be tested for superiority of pimodivir in combination with SOC over placebo in combination with SOC at the 2-sided 5% significance level.

The confirmatory test procedure follows the Serial Gate Keeping strategy as outlined in Section 7 of the FDA's draft guidance on Multiple Endpoints to control the overall type I error at the 5% 2-sided level. The primary and six most important secondary endpoints (listed above) will be tested in the hierarchical order per the 5 steps outlined below. All alphas and p-values specified are 2-sided.

Step 1: Test the primary hypothesis ("Hospital recovery scale at Day 6")

- If the p-value is $\leq 5\%$, continue to Step 2.
- If the p-value is $> 5\%$, stop testing, and no claim will be made.

Step 2: Test first set of 2 secondary endpoints (“Incidence in post-baseline complications” and “Time from start of study drug to hospital discharge”). The Bonferroni-Holm procedure will be applied to control the type I error within Step 2.

- If the smallest of the 2 p-values is $\leq 2.5\%$ and the largest of the 2 p-values is $\leq 5\%$, continue to Step 3.

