- If the p-value for “Incidence in post-baseline complications” is $\leq 2.5\%$ but the p-value for “Time from start of study drug to hospital discharge” is $> 5\%$, stop further testing of the secondary endpoints, and make a claim on “Hospital recovery scale at Day 6” and “Incidence in post-baseline complications”.
- If the p-value for “Time from start of study drug to hospital discharge” is $\leq 2.5\%$ but the p-value for “Incidence in post-baseline complications” is $> 5\%$, stop further testing of the secondary endpoints, and make a claim on “Hospital recovery scale at Day 6” and “Time from start of study drug to hospital discharge”.
- If the smallest of the 2 p-values is $> 2.5\%$, stop further testing of the secondary endpoints, and make a claim on “Hospital recovery scale at Day 6” only.

Step 3: Test second set of 2 secondary endpoints (“Time from ICU admission to ICU discharge” and “Time to return to daily activities”). The Bonferroni-Holm procedure will be applied within Step 3.

- If the smallest of the 2 p-values is $\leq 2.5\%$ and the largest of the 2 p-values is $\leq 5\%$, continue to Step 4.
- If the p-value for “Time from ICU admission to ICU discharge” is $\leq 2.5\%$ but the p-value for “Time to return to daily activities” is $> 5\%$, stop further testing of the secondary endpoints, and make a claim on “Hospital recovery scale at Day 6”, “Incidence in post-baseline complications”, “Time from start of study drug to hospital discharge” and “Time from ICU admission to ICU discharge”.
- If the p-value for “Time to return to daily activities” is $\leq 2.5\%$ but the p-value for “Time from ICU admission to ICU discharge” is $> 5\%$, stop further testing of the secondary endpoints, and make a claim on “Hospital recovery scale at Day 6”, “Incidence in post-baseline complications”, “Time from start of study drug to hospital discharge” and “Time to return to daily activities”.
- If the smallest of the 2 p-values is $> 2.5\%$, stop further testing of the secondary endpoints, and make a claim on “Hospital recovery scale at Day 6”, “Incidence in post-baseline complications” and “Time from start of study drug to hospital discharge”.

Step 4: Test the fifth secondary endpoint (“Time from start to end of mechanical ventilation”)

- If the p-value is $\leq 5\%$, continue to Step 6.

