- If the p-value is $> 5\%$, stop further testing of the secondary endpoints, and make a claim on “Hospital recovery scale at Day 6”, “Incidence in post-baseline complications”, “Time from start of study drug to hospital discharge”, “Time from ICU admission to ICU discharge”, and “Time to return to daily activities”.

Step 5: Test the sixth secondary endpoint (“Rate of re-hospitalization”)

- If the p-value is $\leq 5\%$, make a claim on “Hospital recovery scale at Day 6”, “Incidence in post-baseline complications”, “Time from start of study drug to hospital discharge”, “Time

from ICU admission to ICU discharge”, “Time to return to daily activities”, “Time from start to end of mechanical ventilation”, and “Rate of re-hospitalization”.

- If the p-value is >5%, make a claim on “Hospital recovery scale at Day 6”, “Incidence in post-baseline complications”, “Time from start of study drug to hospital discharge”, “Time from ICU admission to ICU discharge”, “Time to return to daily activities”, and “Time from start to end of mechanical ventilation”.

For the primary endpoint, the results from the proportional odds model will be used in the hypothesis testing. If the proportional odds assumption would not hold on the treatment effect, the p-value from the van Elteren test will be used. For the secondary endpoints time from start of study drug to hospital discharge, time from ICU admission to ICU discharge, time to return to daily activities, and time from start to end of mechanical ventilation, the results of the Gehan-Wilcoxon test will be used in the hypothesis testing. For incidence in post-baseline complications and rate of re-hospitalization the results of the logistic regression will be used. For all these evaluations p-value combination tests will be used, as described below.

The final analysis on the ITT-i set (to support FDA marketing approval) and the final analysis on the OST subset (to support marketing authorization approval in EMA) will be performed independently, using a 5% two-sided significance level for each.

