5.1.2. Statistical Methodology for Evaluation at the Final Analysis

All p-values below are one-sided p-values, to evaluate rejection of the null hypothesis that pimodivir is not better than placebo.

Scenario 1: The final analysis will be performed in the subgroup with time between onset of symptoms and start of treatment between 0 and 72 hours only. P-values for the final analysis will be based on 2 inverse-normal combination tests of p-values as outlined below.

Let:

- p = p-value (one-sided) from full study population of the pre-interim' category of the study period subgroup
- p_1 = p-value (one-sided) from subgroup with time between onset of symptoms and start treatment between 0 and 72 hours of the pre-interim' category of the study period subgroup
- p_2 = $2 * \min(p, p_1)$
- q_1 = p-value (one-sided), from subgroup with time between onset of symptoms and start treatment between 0 and 72 hours on the patients enrolled of the 'post-interim' category of the study period subgroup
- N_1 = actual sample size at interim i.e.:all randomized subjects analysis set (RAND) included in the IA
- N = 600, the initially planned study sample size
- w_1 = $\sqrt{N_1/N}$
- w_2 = $\sqrt{1-(N_1/N)}$
- $\phi^{-1}(x)$ = the inverse of the standard normal cumulative distribution function in x

Note: p_1 and q_1 are based on a subset of subjects with onset of symptoms and start treatment between 0 and 72 hours, and therefore this stratification factor is not included in the respective models.

The p-values resulting from the following 2 combination tests both should be below the pre-specified alpha (2.5% one-sided) to claim superiority in subgroup with time between onset of symptoms and start of treatment between 0 and 72 hours:

$$1-\phi(C(p_1, q_1)) \text{ where } C(p_1, q_1) = w_1 * \phi^{-1}(1-p_1) + w_2 * \phi^{-1}(1-q_1)$$

$$1-\phi(C(p_2, q_1)) \text{ where } C(p_2, q_1) = w_1 * \phi^{-1}(1-p_2) + w_2 * \phi^{-1}(1-q_1)$$

Scenario 2: The final analysis will be performed in the full study population. P-values for the final analysis will be based on 2 inverse-normal combination tests of p-values.

Let additionally:

- q = p-value from full study population on the patients enrolled of the 'post-interim' category of the study period subgroup

The p-values resulting from the following 2 combination tests both should be below the pre-specified alpha to claim superiority in the full study population:

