ICU admission started post-baseline	
Incidence of post-baseline ICU admission
 
 - Admitted to ICU post-baseline - Not admitted to ICU post-baseline 
Note: In case a patient is in the ICU at baseline and (after discharge from the ICU) the patient is re-admitted post-baseline, this subject will be counted as "Admitted to ICU post-baseline".

First admission to intensive care unit (ICU)	
When was the subject first admitted to the ICU during the study?
 
Categories:
 
 - In ICU at baseline - Admitted in ICU Post-baseline - Never admitted to ICU
Time from ICU admission to ICU discharge (hours) [Time-to event]	
The time from max(first admission to ICU, first study drug intake) until the time of first discharge from the ICU.
 
Censoring and calculation of the time will be done analogous to "Time to hospital discharge".
 
Only subjects admitted to the ICU (at any point during the trial) are included in the analysis and analysis is restricted to the first ICU admission.

Time from ICU admission requiredness to ICU discharge readiness (days) [Time-to event]	
The date from max(requiring ICU level of care , first study drug intake) until the date of not requiring ICU anymore(= event), requiring ICU level of care to be defined by the investigator.
 
Censoring and calculation of the time (days) will be done analogous to "Time to hospital discharge"
 
Subjects that do not require ICU level of care will be excluded from this analysis and this analysis is restricted to the first required ICU level of care.

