Total time in intensive care unit (ICU) stay (hours) [Duration]	
The total number of hours a subject stayed in ICU during the period from first intake until study termination, calculated as sum of [(end date and time of discharge-- start date and time of admission)/3600], rounded to one decimal for all separate events per subject
 
In case ICU admission took place before first intake or in case the start datetime of ICU is missing, then the date and time of first intake will be used.
 
In case the ICU stay ended after the end of the trial or in case the end datetime of ICU stay is missing, then the end datetime of last contact date will be used.
 
If time of the start of ICU admission is missing then use 00:00. If time of the end of ICU admission is missing then use 23:59. The derivation of total time in ICU is analogous to “total length of hospital stay”.

Type of supplemental oxygen administration	
Tabulation will be done as collected per CRF page “Oxygen Supplementation”. In addition, the following categorization will be done:
 
 - Invasive Mechanical Ventilation - Non-Invasive Mechanical Ventilation - Non-Invasive, Non-mechanical Ventilation - None
Mechanical ventilation during study	
Incidence of mechanical ventilation (invasive or non-invasive) Categories:
 
 - Mechanical ventilation at baseline - First administration of mechanical ventilation post-baseline - No administration of mechanical ventilation
Mechanical ventilation started post-baseline	
Incidence of post-baseline mechanical ventilation (invasive or non-invasive)
 
 - Started post-baseline - Not started post-baseline 
Note: In case mechanical ventilation is present at baseline and a second episode of mechanical ventilation is initiated post-baseline, this subject will be counted as started post-baseline.

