
Time from start of mechanical ventilation to end of mechanical ventilation (hours) [Time-to event]
	
The time from max(start date and time of first mechanical ventilation, study drug intake) until the end date and time of mechanical ventilation.
 
Note: Invasive and non-invasive mechanical ventilation are considered and are defined on the Oxygen Supplementation form: Type of supplemental oxygen administration. Only the first mechanical ventilation period is considered.
 
Censoring and calculation of the end time will be done analogous to “Time to hospital discharge” if time part of the start of mechanical ventilation is missing then it will be imputed with 00:00.
 
Subjects that are not on mechanical ventilation (at any point during the trial) are excluded from this analysis and this analysis is restricted to the first time mechanical ventilation is used.

Total time on mechanical ventilation (hours) [Duration]
	
The total number of hours of mechanical ventilation during the period from first intake until study termination, calculated as sum of [(end date and time of mechanical ventilation – start date and time of mechanical ventilation)/3600], rounded to one decimal for all separate events per subject
 
In case mechanical ventilation was started before first intake or in case the start datetime of mechanical ventilation is missing, then the date and time of first intake will be used.
 
In case mechanical ventilation ended after the end of the trial or in case the end datetime of mechanical ventilation is missing, then the end datetime of last contact date will be used.
 
If time of the start of mechanical ventilation is missing, then use 00:00. If time of the end of mechanical ventilation is missing, then use 23:59. The derivation of the total time is analogous to “Total length of hospital stay”.

Time to clinical response (hours) [Time-to event]
	
The time to clinical response is defined as the time (in hours) from first study drug intake until the first assessment (actual date and time) of a successive series of 4 recordings (over 5 scheduled successive analysis timepoints, 1 missing timepoint is allowed) where at least 4 of 5 symptoms (temperature, blood oxygen saturation, heart rate, SBP, respiration rate) are normalized, with at least normalization of temperature and blood oxygen saturation.
 
Normalization of clinical response is defined in Table 4.

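### Endpoints 4 and 6 are tested in subjects selected by ICU entry or ventilation that can follow dosing, and endpoint 5 has two rules for deaths without diary records

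*SAP*

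**What the plan says.** **Endpoints 4 and 6.** For time from ICU admission to ICU discharge, SAP Section 5.3.1.1 states: "Only subjects admitted to the ICU (at any point during the trial) are included in the analysis". For ventilation: "Subjects that are not on mechanical ventilation (at any point during the trial) are excluded from this analysis". Each clock starts at first dose or, if later, at ICU admission or start of ventilation, so subjects who first enter after dosing are counted. The any-time restriction is SAP text. Protocol Sections 2.1.2 and 11.4 name these endpoints, and 2.1.2 discards time before study drug, but neither defines the analysis set this way.

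**Place in the testing sequence.** SAP Section 5.1.1 begins: "First, the primary endpoint will be tested for superiority of pimodivir in combination with SOC over placebo in combination with SOC". Complications and time to discharge must then both succeed. Endpoint 4 is next, paired with endpoint 5: "The Bonferroni-Holm procedure will be applied within Step 3". Endpoint 6 follows alone at Step 4. On the final p-values: "For all these evaluations p-value combination tests will be used, as described below". In the full-population branch of Section 5.1.2, the p-values of two combination tests "both should be below the pre-specified alpha to claim superiority in the full study population".

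**Related analyses already planned.** Section 5.3.1.1 sorts subjects by ICU status (baseline, post-baseline, never) and by ventilation status, with a category "Mechanical ventilation at baseline". Section 5.3.2.1 analyses incidence parameters by logistic regression. None of these is in the confirmatory sequence or linked to the reading of endpoints 4 and 6.

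**Endpoint 5.** Section 5.3.1 sets one rule for time-to-event variables: a subject who dies before the event is censored at the longest time seen in any subject. Section 5.3.1.3, on time to return to daily activities, leaves out anyone with no post-baseline record and makes no exception for death. Protocol Section 9.2.1.3 says incapacitated or intubated subjects do not complete the questionnaires.

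**The concern.** For endpoints 4 and 6, membership of the analysis set is itself something treatment may change. Suppose pimodivir keeps the sickest patients out of ICU and does nothing to the length of a stay. The pimodivir ICU group then holds a milder mix, and its stays look shorter. Preventing severe admissions is a real benefit, but it is not the benefit the claim would state. These tests open only after the primary endpoint, complications and discharge have all succeeded, which is also when an effect on admission is most plausible.

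For endpoint 5, two programmers following different sections could build different analysis sets for a confirmatory test.

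**Working it through.** **1. The plan's own sample size.** Inputs (SAP Section 1.4): placebo Day 6 distribution 30/30/25/5/5/5%, common odds ratio 0.62, two-sided 5%, 90% power. With N = 12(z0.975 + z0.90)² / [(1 - Σp̄³)(ln OR)²], the result is N = 601.4, and power at 600 is 89.9%. The stated 600 and 90% are reproduced. The documents give no sample size, power or event count for endpoints 4 to 6.

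**2. What that effect implies for ICU and ventilation.**
- Category 4 or worse: odds 0.15/0.85 × 0.62 = 0.1094, so 15% becomes 9.86%.
- Death: 0.05/0.95 × 0.62 = 0.0326, so 5% becomes 3.16%.
- Categories 4 and 5 together, per 300: 30 on placebo and (0.0986 - 0.0316) × 300 = 20.1 on pimodivir.

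This is a Day 6 snapshot that mixes fewer admissions with earlier discharge. It shows only that sets of unequal size are plausible.

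**3. False shorter-stay rate for endpoint 4.** Stay length depends only on severity, and the drug changes only post-dose admission.

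From the documents: 300 per arm, 75% treated within 72 hours, the Gehan-Wilcoxon test, and the full-population rule of Section 5.1.2. Under that rule p2 = 2·min(p, p1), w1 = √(N1/600), and both C(p,q) and C(p2,q) must pass.

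Assumed:
- N1 = 400, so w1 = √(400/600) = 0.816.
- 5-20% in ICU at baseline, and 5-20% of the rest admitted later on placebo.
- Admission odds ratio 0.62, borrowed from the primary endpoint.
- Half of admissions mild (mean stay 3 days, 2% die) and half severe (mean 8 days, 20% die), with exponential stays.
- For the stratified runs, NEWS2 of 6 or more in 75-90% of severe and 30-40% of mild admissions.

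At 10% baseline and 10% later, placebo has 30 + 27 = 57 ICU subjects. On pimodivir, odds 0.1111 × 0.62 = 0.0689 give 6.4% of 270, or 17.4, so 47 in all. About 9.6 admissions are prevented. If all are severe, severe admissions fall by 9.6/13.5 = 71%. If 75% are severe, severe fall by 53% and mild by 18%.

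Rates of a pimodivir-favouring result against one-sided 2.5%:

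| Admissions prevented | 10%/10%, unstratified | 10%/10%, NEWS2 strata | 5%/20%, unstratified | 5%/20%, NEWS2 strata |
|---|---|---|---|---|
| none | 1.5% | - | - | - |
| in proportion | 1.4% | - | - | - |
| 75% severe | 2.4-3.1% | 2.0-2.6% | - | - |
| all severe | 4.1-4.7% | 3.1-3.9% | 9.4-11.3% | 5.3-7.9% |
| mild only | 0.4% | - | - | - |

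A dash means no figure is given here. Ranges cover repeated runs and, for the stratified columns, the NEWS2 assumption. Monte Carlo error is about 0.2-0.3 points near 2.5%. The undistorted rate is below 2.5% because both combinations must pass. With N1 of 300 or 450, the unstratified all-severe rate at 10%/10% is 4.0-4.8%. With only mild admissions prevented, power for a halved stay falls from 52% to 29% (unstratified).

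**4. Endpoint 6.** Assumed 5%/5%: placebo 15 + 14.25 = 29 and pimodivir 15 + 9.0 = 24 subjects. Unstratified rates are 1.5% (unaffected), 2.4% (75% severe) and 3.2% (all severe).

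**5. Subjects already in ICU at first dose.** Tested alone, this set stayed at 2.1-2.9% in all 36 settings examined, because treatment cannot change its membership.

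**6. Endpoint 5.** Day 6 deaths are 0.05 × 300 = 15 on placebo and 0.0316 × 300 = 9.5 on pimodivir. If 25-100% of them have no diary record (assumed), Section 5.3.1.3 drops about 4-15 and 2-9.5. With no effect in survivors, the mean Gehan z (positive favours pimodivir) is -0.02 to 0.38 with those deaths dropped and 0.34 to 0.48 with them kept.

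**The case against.** **Size.** A marked preference, with severe admissions down 53% and mild down 18%, only brings the planned test to about nominal at 10%/10%. A clear excess there needs severe admissions to fall by 71% with no mild one prevented. The planned test is stratified by factors that include NEWS2, and this lowers the rates. Every ICU input is assumed. All of this stands, and the stratified figures are the ones to use. Stratification reduces the effect and does not remove it.

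**Gates.** The rates are for the test alone, and the earlier steps were not simulated, so they are not overall chances of a false claim. This stands.

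**Already disclosed.** Incidence of post-baseline ICU entry and ventilation is planned, and the primary endpoint scores ICU, ventilation and death in all infected treated subjects. What is missing is an estimate of stay in a set fixed before treatment.

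**A condition on the claim.** One could allow a shorter-stay claim only if baseline entrants point the same way. In unstratified runs that moves the all-severe rate only from 4.7% to 4.6% at 10%/10%, and from 9.4% to 7.9% at 5%/20%. Requiring one-sided p ≤ 0.10 in baseline entrants gives 3.2% in both, but cuts power for a halved stay from 52.1% to 44.1% and from 62.2% to 33.1%. Neither should be required.

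**Endpoint 5.** Section 5.3.1.3 can be read as saying who is analysed, and Section 5.3.1 as saying how deaths among them are censored. That reading is possible, but the SAP does not state it, and Section 5.3.1 has no exception for subjects without records.

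**Conclusion.** The selection in endpoints 4 and 6 is real, and its consequence is conditional. There is no distortion if admission is unaffected or prevented in proportion, and power is lost if mild admissions are prevented. The false-result rate rises only if severe admissions are strongly preferentially prevented: at test level with NEWS2 strata, about 3-4% at 10%/10% and 5-8% at 5%/20% when all prevented admissions are severe. Unstratified, the figures are 4-5% and 9-11%. They rest on assumed ICU rates, severity mix and stay lengths.

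A reader might infer that these two tests generally exceed their error rate, or that the efficacy conclusion is at risk. The documents do not support either: they give no severity mix for admissions, and the primary endpoint avoids this selection. Nor is the any-time set a protocol definition.

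For endpoint 5, a reader might infer that all early deaths are dropped, or that the rule flatters pimodivir. Only deaths with no post-baseline daily-activity record are affected, whenever they occur. If pimodivir lowers mortality, dropping them works against it. The effect is small, but the two sections need reconciling.

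**What to change.** **Endpoints 4 and 6.** Keep both tests. In the SAP, pre-specify a supporting analysis of each, with confidence interval, in subjects whose ICU stay or ventilation began before first study drug intake. Define them by start date-time and not by baseline hospital recovery scale, because Section 2.5 says: "The baseline HRS is defined irrespective of the time of the start of study drug". Report it beside the planned all-subject incidence of post-baseline ICU admission and ventilation, and say that both will be used in interpreting a shorter-stay or shorter-ventilation result.

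**Endpoint 5.** In Section 5.3.1.3, state that subjects who die without a post-baseline record are kept and censored at the maximum time, as in Section 5.3.1. Other subjects without records are censored at Day 1, as Section 5.3.1.2 does for viral negativity. In a Gehan test this is practically the same as excluding them. Since subjects without records would then carry information only if they died, add a sensitivity analysis excluding all of them.

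**Cost.** One SAP amendment before unblinding, with endpoints, tests and testing sequence unchanged. The supporting analysis will be imprecise: 0.05 × 300 = 15 to 0.10 × 300 = 30 per arm for ICU if 5-10% are there at baseline (assumed), and fewer for ventilation. For endpoint 5, simulations with no treatment effect, deaths kept and other no-record subjects excluded gave one-sided rates of 2.0-2.6% favouring pimodivir and 2.4-2.9% favouring placebo, with 0-40% of survivors giving no diary data.
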